
Data analysis: During the training sessions we will use the imaging data in real time to feedback information about the brain state (where in a continuum from CALM to STRESS the participant is a each moment) for the participant to use mental strategies (think happy thoughts, breath deeply, imagine a quiet place, etc) to try to bring the thermometer toward CALM. As the thermometer moves to CALM, the environment will be manipulated toward less stressful images and sounds. We hypothesize that over time, participant's brains will accommodate to expect that these mental strategies effectively change the environment toward being calmer and safer. This may translate into such strategies becoming more and more useful in real life. The main data to be analyzed will be whether PTSD symptoms (as measured by questionnaires) decrease over time.

In an exploratory manner, some participants may explore the Virtual Iraq (and calm environments) while wearing a commercially available one-electrode eeg. This is similar to headphones and gives an eeg signal that will be analyzed to study the possibility of discerning the signal while under stress (Virtual Iraq) and calm epochs. This will last no more than 15 minutes and data will be analyzed for each individual, solely to verify feasibility for future studies.

Section G: Sample Size/Data Analysis

G1. Sample Size

How many subjects (or specimens, or charts) will be used in this study?

Local: 35 Worldwide: 35

Please indicate why you chose the sample size proposed:

There is no data available to calculate sample size. This will be a pilot to study the possibility that the proposed approach merits further study.

G2. Data Analysis

Provide a description of your plan for data analysis. State the types of comparisons you plan (e.g. comparison of means, comparison of proportions, regressions, analysis of variance). Which is the PRIMARY comparison/analysis? How will the analyses proposed relate to the primary purposes of your study?

The primary outcome will be clinical data from CAPS scores before and after the procedure.

In addition, we will use activity monitors (similar to a commercially available FitBit) that will be used by subjects from at least a week before the study starts, to at least a week after the last MRI session. This will allow us to study not only diurnal activity, but also quality of sleep, a major problem for PTSD patients.

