
extremities, except for patients with impaired systemic blood flow and/or perspiration. We will adhere to the recommendations for the head. The scanner has a large monitor indicating the RF power level which can be limited to a specific maximum.

Risks associated with trauma exposure PTSD patients may feel stress and anxiety when exposed to "Virtual Iraq". However, we will avoid recruiting patients with a caps score higher than 3, which will minimize the possibility of a serious reaction to the scenes. In addition, PTSD patients are routinely exposed to therapies in which stressful events are recalled (including Virtual Iraq, which we will use in this application), usually with positive consequences. Patients will be debriefed and asked how they are doing. If they report extreme anxiety or agitation they will need to be held until they feel better.

The eeg pilot (to be performed only on some participants as a pilot to study the possibility of using eeg in the future in similar protocols) adds no risk to the protocol. The eeg electrode to be used feels just like wearing headphones. There is no known risk associated to wearing the electrode, which is sold and marketed as a toy suitable even for children.

H2. Data and safety monitoring plan

Do the study activities impart greater than minimal risk to subjects? No

H3. Coordination of information among sites for multi-site research

Is the BCM Principal Investigator acting as the SPONSOR-INVESTIGATOR for this multi-site research?

No or Not Applicable

Is BCM the COORDINATING CENTER for this multi-site research?

No or Not Applicable

Section I: Potential Benefits

It is possible that these procedures result in individual personal strategies to avoid feeling stress in PTSD patients. This is exactly what we want to measure. Patients will also receive a small monetary compensation.

Describe potential benefit(s) to society of the planned work.

The potential benefits to society are quite large: If our trial is successful, this method could result in a major improvement on exposure therapies, and in the acquisition of a large body of knowledge in terms of the brain mechanisms of PTSD and its recovery.

Do anticipated benefits outweigh potential risks? Discuss the risk-to-benefit ratio.

The risks are minimal, being that the MRI is very safe (we have scanned thousands of patients with no adverse events) and exposure therapy has been performed in thousands of veterans.

Section J: Consent Procedures

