Interview and questionnaires: Next, you will participate in a structured interview regarding past and present difficulties you may have had. You will also be asked to complete some questionnaires. The purpose of this interview and the questionnaires is to determine that you qualify for the study. This visit lasts between 2-4 hours.

Virtual reality training sessions: Veterans will participate in 1-2 functional magnetic resonance imaging (fMRI) sessions at the Core for Advanced Magnetic Resonance Imaging (CAMRI) at Baylor College of Medicine. During these sessions, you will be exposed to a virtual reality combat scenario while your brain activity is monitored. Information will be collected throughout the scanning session about your stress response to various stimuli. Sessions last about 1-2 hours. fMRI is non-invasive and should not cause discomfort. Unlike x-rays or CT scans, fMRI does not involve exposure to radioactive material.

Study: PTSD Virtual World fMRI Training

Feedback sessions: Next, Veterans may participate in up to 6 feedback sessions. Similar to the training sessions, you will view virtual reality combat scenarios while your brain activity is monitored in a fMRI machine. During these sessions, however, you will be provided constant feedback on your stress levels to help you bring your stress levels down. We anticipate these sessions to last about 1-2 hours.

Ongoing assessment: Veterans will fill out a number of self-report questionnaires throughout the course of the study. You will also be given 1-2 wearable sensors to monitor your sleep quality, heart rate, and physical activity during the course of the study.

Mode of Advertising: BCM Clinical Trials Website

Exact language of Advertisement:

Research Study for US veterans suffering from PTSD. We are investigating how the brain functions in PTSD and how to modulate its activity. If interested, please call [contact] or email [contact]. Compensation available.

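### The plan names distress from the virtual scenes as a risk but does not plan to record, count or report acute distress, participant-stopped scans or individual symptom worsening

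*Combined protocol and SAP*

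**What the plan says.** **The risk.** H1, under trauma exposure, says that PTSD patients may become stressed or anxious in the virtual environment. It relies first on an entry limit: "we will avoid recruiting patients with a caps score higher than 3, which will minimize the possibility of a serious reaction to the scenes". After exposure, "Patients will be debriefed and asked how they are doing", and "If they report extreme anxiety or agitation they will need to be held until they feel better". F2 adds a therapist during the office training and a squeeze ball for stopping a scan. H2 contains "Do the study activities impart greater than minimal risk to subjects? No", and no monitoring plan follows.

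**The analyses.** F2 says "The main data to be analyzed will be whether PTSD symptoms (as measured by questionnaires) decrease over time". G2 says "The primary outcome will be clinical data from CAPS scores before and after the procedure". The other analyses are activity and sleep from wearable monitors, a general linear model of brain regions on aggregate imaging data, and an exploratory EEG feasibility check made person by person. The flier in Section R adds "Veterans will fill out a number of self-report questionnaires throughout the course of the study".

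**Design.** There is no placebo group (F1). The sample size is 35, with no calculation (G1). Healthy controls are included for testing procedures (F1), but their number is not given.

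**The concern.** The steps in H1 and F2 manage distress when it happens. None of them turns it into data. The documents do not say that debrief answers, episodes of extreme anxiety or agitation, or uses of the squeeze ball are written down, and no analysis in F2 or G2 would use them. Nor does any analysis identify patients whose CAPS or questionnaire scores went up.

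Two different harms are left out. One is an acute reaction during or just after exposure, which is what H1 describes. The other is a higher symptom score after the course of sessions than before it. Neither measures the other, so each needs its own line in the report.

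G1 says the pilot is to show whether the approach is worth pursuing, and Section I weighs benefit against risk. Followed as written, the plan supplies evidence for the first side only. Worsening on CAPS could still be extracted later from stored scores, but with a threshold chosen after seeing them. Debrief answers and stopped scans that were never written down cannot be recovered.

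**Working it through.** **1. Is there a plan to capture or report these harms?**

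| Item | What the documents provide | Recorded, counted or reported? |
|---|---|---|
| Acute stress or anxiety | Entry limit, therapist at office training, debrief, holding (H1, F2) | Not stated |
| Scan stopped by participant | Squeeze ball (F2) | Not stated |
| CAPS worsening | CAPS before and after (G2) | Scores collected; no individual rule |
| Questionnaire worsening | Repeated self-report (Section R); F2 asks about a decrease | Scores collected; no individual rule |

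**2. Could a mean hide worsening?** The plan has no figure to reproduce: G1 gives 35 without effect size, SD, alpha or power, and no test is named for CAPS. What follows is illustration under assumptions.

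Suppose k of n = 35 patients change by +1 unit and the rest by −1 unit, with residual SD w between 0 and 0.5 units. The t statistic does not depend on the size of the unit.

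- Mean m = (k − (35 − k))/35.
- Between-patient variance v = [k(1 − m)² + (35 − k)(−1 − m)²]/34.
- t = m / (√(v + w²)/√35), on 34 degrees of freedom.

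For k = 7, m = (7 − 28)/35 = −0.60 and v = (7 × 2.56 + 28 × 0.16)/34 = 0.659. With w = 0, t = −0.60/(0.812/5.916) = −4.37.

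| Worsened | Mean change | t (w = 0 to 0.5) | Two-sided p |
|---|---|---|---|
| 5/35 | −0.71 | −5.95 to −4.87 | below 0.0001 |
| 7/35 | −0.60 | −4.37 to −3.72 | 0.0001 to 0.0007 |
| 10/35 | −0.43 | −2.77 to −2.43 | 0.009 to 0.021 |

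With more noise (true changes of ±1 SD, individual noise SD 1), simulation of a two-sided paired t-test at 0.05 gives a significant decrease in about 82% of trials when 7 of 35 worsen and about 95% when 5 of 35 do. If only 20 PTSD patients are evaluable (an assumption) and 4 worsen, it is about 50%.

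**3. How much of a raw count is noise?** If changes are normal with a standardised mean decrease d, the share scoring higher afterwards is Φ(−d): 38% for d = 0.3, 31% for 0.5 and 21% for 0.8. Of 35 patients that is about 13, 11 and 7. Part of this is measurement error, so a count needs a margin.

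**4. What would a count deliver?** Exact (Clopper–Pearson) 95% limits are:

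- 0/35: 0% to 10.0% (upper limit 1 − 0.025^(1/35)).
- 5/35 = 14.3%: 4.8% to 30.3%.
- 7/35 = 20.0%: 8.4% to 36.9%.
- 0/20: upper limit 1 − 0.025^(1/20) = 16.8%.

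The chance of seeing at least one event is 1 − (1 − p)^n. At true rates of 2%, 5% and 10% it is 51%, 83% and 97% for n = 35, and 33%, 64% and 88% for n = 20.

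**The case against.** A reader might infer that the plan averages worsened patients away by looking only for a group decrease. The documents do not support that. No mean, test or group summary is named for CAPS or the questionnaires. The CAPS wording in G2 has no direction and could show an increase. The one-directional wording is confined to the F2 sentence, and aggregate data are mentioned only for the imaging model. The plan is unspecified, not committed to averaging, so masking is a possibility and not a consequence of the text.

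A reader might also call patients who worsened harmed by the procedure. With no control arm that cannot be said; the same limit applies to any improvement.

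Further objections stand in part:

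- Some stress is intended, because the scenes are built to provoke it. That is a reason to define which reactions are tabulated, not to leave them all out.
- The score illustrations say nothing about acute distress, the harm H1 actually names. They bear only on symptom worsening.
- The eligibility text cites only single-digit CAPS values and does not say which CAPS score is analysed. A roughly normal change is therefore an assumption.
- Tabulating distress is not free reuse of existing data. H1 sets no debrief schedule, and Section J1 places a debrief after participation. Some new recording is needed.

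None of this supplies the missing plan to record and report.

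**Conclusion.** The point holds in this form: H1 names the risk, F2 frames the main symptom question as a decrease, and the documents contain no plan to record, count or report acute distress, participant-stopped scans or individual worsening. This rests on the text and needs no assumption. It should be corrected, because the conclusion about further study would otherwise draw on benefit data only.

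The size of any masking is conditional. It requires that a mean change is used, and it rests on assumed effects, noise and worsening rates. The drop from about 82% to about 50% between 35 and 20 patients shows how strongly it depends on the unstated number of PTSD patients. The illustrations do not predict how many will worsen. A count from this study will be imprecise: even no event among 35 is compatible with a true rate of up to 10.0%, and among 20 with up to 16.8%.

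**What to change.** Add to G2:

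1. Beside the before-and-after CAPS result, show individual changes. Report the number and proportion of PTSD patients whose CAPS rose by more than a margin fixed before any post-treatment CAPS is viewed, with an exact 95% confidence interval. Describe this as worsening observed, not attributed to the procedure.
2. For the questionnaires, do the same at the final assessment only. Do not use each patient's worst later score: with no true change and independent, equal noise, the worst of k later scores exceeds baseline with probability k/(k + 1), which is 75% for k = 3 and 86% for k = 6.
3. As a separate outcome, write on the session record, and tabulate by session type (office, training scan, feedback scan), each report of extreme anxiety or agitation, each scan stopped by the participant, and each related withdrawal.
4. State that the conclusion on further study uses the benefit and harm results together, and give the number of PTSD patients behind each proportion.

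Cost: a few sentences in G2, one table, and a short new entry on the session record. No visits, procedures or participants are added. The downside is that the counts will be imprecise and will include some measurement noise. No change to exposure, stopping or care is proposed.

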We aim to improve the treatment of PTSD using a combination of virtual worlds and neuro-feedback. Virtual worlds have been used to successfully treat PTSD induced by combat experience for a subset of the population. The primary approach is called extinction therapy, in which carefully controlled stimuli is used to evoke the associative memory of the original trauma. By maintaining the intensity of the patient response at a level the patient can comfortably tolerate, the sensitivity for triggering the traumatic response as well as the strength of the response can be gradually reduced with repeated treatments. However, given the variety of patient responses, modulating the stimulus optimally over the course of a treatment session is elusive. What is required is a real-time neuro-feedback system that can continually measure the degree of traumatic state of the patient, and then automatically control the stimulus to maintain the stress response within an effective therapeutic range. The purpose of this pilot project is to approach this goal by applying recent basic research we have conducted jointly at UT Austin and BCM on analyzing brain states using fMRI data with machine learning algorithms while exposing the subject to real-time virtual worlds. This pilot will extend that work to real-time neurofeedback applied to treatment of PTSD. Using fMRI for neuro-feedback, rather than the much more common EEG, should enable a significantly increased accuracy in the assessment of the patient; s current neuro-cognitive state. It should also lead to a better understanding of the neurophysiology during a stress response, e.g. which brain regions are most involved. This is not necessarily the same as which brain regions are the most active. Our analysis technique takes the next step by measuring the degree to which brain regions are critical to discriminating between different brain states, such as threatened versus safe.

Section E: Protocol Risks/Subjects

E1. Risk Category

Category 1: Research not involving greater than minimum risk.

E2. Subjects

Gender:

Both

Age:

Adult (18-64 yrs)

Ethnicity:

All Ethnicities

Primary Language:

English

Groups to be recruited will include:

Patients

Which if any of the following vulnerable populations will be recruited as subjects?

Mentally ill

Vulnerable populations require special protections. How will you obtain informed consent, protect subject confidentiality, and prevent undue coercion?

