Subjects will be first assessed and screened for eligibility and safety. As part of the screening process, a CAPS-5 PTSD clinician administered assessment will be administered. This administration may be recorded for validity purposes, in which chase data would be stored using a VA-approved secure portable USB device. These data will be destroyed at the conclusion of the study. Study participants will sign VA forms 10-3203 and 10-5345 for these purposes. The next step is an evaluation in a specially-equipped lab of appropriate stimulus parameters to evoke a stress response in each subject. The subject will interact with an audiovisual stimulus called Virtual Iraq, a commercially available virtual-world environment. The interaction involves passive view of a virtual town with an appearance similar to those found in Iraq. Events will occur in the stimulus designed to evoke stress, such as smoke, explosions, or the appearance of enemy combatants. The level of stress elicited by the virtual world will be manipulated using controls in the stimulus package specifically designed to vary threat levels. Patients will undergo this training in the presence of an experienced PTSD therapist, who will gradually guide the patient through a gamut of stress levels that remains at tolerable levels. Calm environments (such as a nice beach) will also be explored by the participants. Once we verify that all subjects can be safely exposed to this virtual world, they will be scanned using functional MRI under stimulus conditions that vary over a gamut of conditions varying from nonthreatening to strongly threatening. The MRI scanner we will use differs from conventional scanners only in that the magnet strength is 3 T, rather than the more typical 1.5 T magnets used in routine clinical scanning. The subject will enter a large room where a powerful magnet is located. Subject will be instructed to remove all jewelry and other metalcontaining objects. The subject will then be placed on a narrow table with plastic-encased metal coil close to the head. Next, the subject will be slid into a small tunnel approximately 6 feet long and 24 inches in diameter. The duration of the scan is approximately 70 minutes. A small mirror with a filter holder to enable 3D stimulation will be positioned above the subject's head so they can view a 3D LCD display at the opposite end of the scanner. After the subject is positioned, the table will move the subject into the scanner itself. Subjects will wear MR-compatible headphones for audio stimulation, and for voice-communication with a technician or investigator. They will also be given a pneumatic squeeze ball which they will instructed to use to signal that scanning should be stopped at any time. Subjects will participate in 3--8 scanning sessions. Brain imaging data will be collected and analyzed using machine learning techniques to discriminate a range of brain states varying from ¿non-threatening¿ to ¿highly threatening¿. The first 1--2 sessions will be used to ¿train¿ a software analysis program to recognize the subject; s brain states. Once these two states have been determined, subjects will be scanned during 1--6 feedback sessions, using similar stimulus conditions, but this time a "thermometer" will display, in real time, the current brain state threat level. Subjects will be instructed to use their mind to bring the thermometer toward the "non-threatening" state. Once the subject is able to move the thermometer toward sufficiently non-threatening "temperatures" the display will briefly change to a pleasing and comfortable image to provide positive feedback. Data storage in a VA repository will be a requirement of the study. Data will be stored in a VA repository (a folder within the S drive in which the imaging data will be stored) on the S drive. This repository is only not to lose data possibly necessary in the future analysis. It will not be released to other investigators unless thei have their own IRB approval prior to coming and asking for these data, including if the investigators of this study decide to do any further research unrelated to this study protocol. Participants will be free to withdraw their data from the study at any point.

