Finally, we will use general linear model analysis on aggregate data to determine if there are specific brain regions in which activity is higher or lower during the two brain states (Threat and Non-Threat). This data may render information important to design and improve PTSD therapy (pharmacological or otherwise) in the future.

Section H: Potential Risks/Discomforts

H1. Potential Risks/Discomforts

Describe and assess any potential risks/discomforts; (physical, psychological, social, legal, or other) and assess the likelihood and seriousness of such risks:

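### Does G2 leave out the regional discrimination measure that Section D describes?

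*Combined protocol and SAP*

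**What the plan says.** Section D lists improved neurophysiological understanding as an expected by-product of using fMRI: "It should also lead to a better understanding of the neurophysiology during a stress response, e.g. which brain regions are most involved". It then adds "This is not necessarily the same as which brain regions are the most active", and continues: "Our analysis technique takes the next step by measuring the degree to which brain regions are critical to discriminating between different brain states".

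F2 describes the scans. Subjects are "scanned using functional MRI under stimulus conditions that vary over a gamut of conditions varying from nonthreatening to strongly threatening". On analysis it says "Brain imaging data will be collected and analyzed using machine learning techniques to discriminate a range of brain states". The first one or two of three to eight sessions train the software to recognise each subject's states. Then "Once these two states have been determined, subjects will be scanned during 1--6 feedback sessions", with a thermometer showing the decoded state. When a subject succeeds, "the display will briefly change to a pleasing and comfortable image to provide positive feedback". The data-analysis paragraph of F2 adds that the scene becomes less stressful as the thermometer moves towards calm.

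G2 names three items: CAPS pre and post as the primary outcome, activity-monitor data, and the imaging analysis, in which "we will use general linear model analysis on aggregate data to determine if there are specific brain regions in which activity is higher or lower" between the two states. Only the third is regional.

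**The concern.** Section D itself says that importance for discrimination and level of activity are different things, and G2 then plans only the second. F2's classifier is described as recognising states and driving the thermometer; no regional output, summary across subjects or test is given for it. An analyst following G2 alone would report an activity map and nothing on discrimination.

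The model in G2 is also thinly described. It does not say which scans are aggregated, or how a graded range of presented threat becomes two labels. The scans differ in kind: in feedback sessions the decoded state helps to set what the subject sees, while in the first one or two sessions it does not. If all scans were pooled, the activity contrast would mix these two situations. At stake are the content and interpretation of the mechanistic findings, not the clinical result.

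**Working it through.** The plan gives no figure for this point, so there is nothing to reproduce. Three checks apply.

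**1. Can the two regional quantities differ?** Take two regions with unit variances and correlation ρ. Let the Threat minus Non-Threat mean difference be d = (1, 0): 1 SD in region A and none in region B. These values are assumed for illustration. The linear discriminant weights are w = Σ⁻¹d = (1, −ρ)/(1 − ρ²). The separation is D = √(d′Σ⁻¹d) = 1/√(1 − ρ²), and the best accuracy with equally frequent states is Φ(D/2).

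| ρ | weight A | weight B | D | accuracy, A and B | accuracy, A alone |
|---|---|---|---|---|---|
| 0 | 1.00 | 0 | 1.00 | 0.6915 | 0.6915 |
| 0.3 | 1.10 | −0.33 | 1.05 | 0.6999 | 0.6915 |
| 0.6 | 1.56 | −0.94 | 1.25 | 0.7340 | 0.6915 |
| 0.8 | 2.78 | −2.22 | 1.67 | 0.7977 | 0.6915 |

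Region B has zero activity difference in every row, yet its weight reaches −2.22 and accuracy rises by up to 0.7977 − 0.6915 = 0.1062. So Section D's distinction is sound: a linear model of activity does not deliver the discrimination measure. This shows the difference is possible; it does not estimate a loss in this study.

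**2. How mixed would pooled scans be?** F2 allows t = 1 or 2 sessions before feedback and f = 1 to 6 with feedback, with 3 ≤ t + f ≤ 8.
- t = 1 permits f = 2 to 6: 5 splits.
- t = 2 permits f = 1 to 6: 6 splits, so 11 in all.
- f exceeds t in 9 splits, equals it in 1 (2, 2) and is below it in 1 (2, 1).
- The feedback share f/(t + f) runs from 1/3 = 33% (2, 1) to 6/7 = 86% (1, 6).

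These counts are unweighted, because the document does not say how often each split occurs. They describe what pooling would involve if it were done, and do not bear on whether a discrimination measure is missing.

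**3. Does the text lead to the feared result?** Set the sections side by side.
- *The measure.* Section D attributes it to the team's own technique, in a paragraph about the group's machine-learning work on brain states. F2 plans machine learning on these scans. The parent analysis is therefore in the plan, and regional importance can be drawn from it. Its absence from G2 does not show that it would go unreported.
- *The scans.* G2 does not say that sessions with and without feedback are combined. Aggregation may simply mean a group-level analysis across subjects, as opposed to the per-subject classifier in F2.
- *The labels.* G2's two states match F2, where the two states are settled in the first one or two sessions before feedback begins. Their origin is given; the cut-points are not.

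**The case for a change.** The strongest case for a change is that G2's own form prompt asks how the proposed analyses relate to the study's purposes, and the technique is described under the purposes heading. A named output and a sentence on scans and labels would cost only analysis time. Without them, both choices stay open until the data have been seen. If the classifier's own output supplied the labels, activity would be tested against labels derived from that activity. The wording adds to the doubt: the data-analysis paragraph of F2 uses the term training for sessions with feedback, while the flier in Section R uses it for the sessions before feedback.

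Much of this stands as description. G2 does not name the output, the scans or the cut-points, and the session terms are inconsistent. But each harm needs an extra step that the document does not take: that the machine-learning work yields no regional result, that all sessions are pooled, or that decoded labels are fed back into the model. An imaging analyst would ordinarily label by presented condition and keep scans with and without feedback apart.

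A prescribed discrimination map would not clearly settle the matter either. With labels set by presented condition it would contrast combat scenes with calm ones, so a region could score highly for sensory reasons. The document also gives no run or block structure from which to judge whether cross-validation within one or two sessions is feasible.

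**Conclusion.** The mismatch between Section D and G2 is genuine but minor, and it calls for no change. It is missing detail about a secondary output, which Section D mentions as an expected by-product and G2 treats as information for designing later therapy. The CAPS comparison does not depend on it. No stated rule gives a wrong answer, and no error in any reported quantity can be derived from the text. The split counts and the two-region example do not measure a loss.

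This rests on two readings: that the machine-learning analysis in F2 is the technique meant in Section D, and that aggregation in G2 does not commit the analysts to pooling sessions with and without feedback. Both fit the text, though neither is spelled out. If either proved wrong, the effect would be confined to exploratory regional findings in a pilot of 35 subjects for which no sample-size calculation was made. Such findings could only suggest hypotheses in any case.

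### G2 compares regional activity between Threat and Non-Threat brain states without saying how scans are labelled; labels taken from the decoder, or from scenes the decoder drives, would make the comparison circular

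*Combined protocol and SAP*

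**What the plan says.** The last analysis in G2 is announced as follows: "we will use general linear model analysis on aggregate data to determine if there are specific brain regions". The contrast it draws is whether "activity is higher or lower during the two brain states (Threat and Non-Threat"). G2 does not say how a scan is assigned to a state, which sessions enter, or whether participants are fixed or random effects.

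F2 supplies the vocabulary. "Brain imaging data will be collected and analyzed using machine learning techniques to discriminate a range of brain states"; the first one or two sessions train a "software analysis program to recognize the subject; s brain states"; and then "Once these two states have been determined, subjects will be scanned during 1--6 feedback sessions". The stimulus is described in other words. Its level is varied with "controls in the stimulus package specifically designed to vary threat levels", and participants are scanned "under stimulus conditions that vary over a gamut of conditions varying from nonthreatening to strongly threatening". For the feedback sessions, the data-analysis paragraph of F2 adds: "As the thermometer moves to CALM, the environment will be manipulated toward less stressful images and sounds".

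G2 makes CAPS before and after the procedure the primary outcome, so the regional analysis is secondary.

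**The concern.** If Threat and Non-Threat are the decoder's output, scans are sorted by a function of regional activity, and regional activity is then compared between the sorted groups. A region can differ because it moves with the decoder score, whether or not it responds to threat. The resulting map would mix response to threat with association with the decoder.

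If the labels describe the scene instead, the problem remains wherever the thermometer changes the scene, because the scene then depends on brain activity a moment earlier. G2 excludes no session.

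At stake is one of the aims in section D, a better understanding of the neurophysiology of the stress response. G2 also expects this result to help in designing future therapy, and inflated or spurious regional effects would carry over into that work.

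**Working it through.** **Inputs.** From the documents: 35 participants; 1–2 training and 1–6 feedback sessions, 3–8 in total. The documents give no decoder algorithm, training labels, region count, volume count, alpha or group model, so there is no planned figure to reproduce. Assumed for illustration: 20 regions, 400 independent volumes per session, half in each preset condition, a linear decoder applied to a new session and split at its median, two-sided 0.05 per region, 60 runs.

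**1. Share of sessions in the feedback loop.** Smallest: 1/(2+1) = 33%. Largest: 6/(1+6) = 86%. Full programme: 6/8 = 75%.

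**2. Bias in a region that does not respond to threat.** Let r be the correlation, within a stimulus condition, between the region and the decoder score. Let the score have mean ±m and SD σ in the two conditions. Splitting scans on the score gives an expected contrast, in SD units, of

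2·√(2/π)·r·exp(−m²/2σ²) = 1.596·r·exp(−m²/2σ²).

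With preset labels the expected contrast is 0.

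**3. Pure noise, within one person.** Here m = 0. With 20 independent regions a typical r is 1/√20 = 0.224, so a typical contrast is 1.596 × 0.224 = 0.357 SD. Its standard error is √(1/200 + 1/200) = 0.10. If r varies normally around 0, the observed contrast has SD √(0.357² + 0.10²) = 0.371, and the share beyond 1.96 × 0.10 = 0.196 is P(|Z| > 0.528) ≈ 60%. Simulation gave 61% with decoded labels and 5.0% with stimulus labels.

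**4. Pure noise, group level.**
- Person-specific decoders, random-effects test: 4.3% of regions, which is nominal, because the chance weights differ in sign between people.
- One decoder shared by all participants: 93%.
- Person-specific decoders pooled with fixed effects: 13–46%, over 20–100 regions and 100 or 200 volumes.
- Stimulus labels, random-effects test: 4.9%.

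**5. Some regions truly respond.** Suppose 3 of 20 regions respond at 0.8 SD, regions correlate at 0.3, and a diagonal classifier weights the three responders equally at 0.8.
- Covariance of a null region with the score: 0.3 × 3 × 0.8 = 0.72.
- σ² = 0.64 × (3 + 6 × 0.3) = 3.07, so σ = 1.753 and r = 0.72/1.753 = 0.411.
- m = 3 × 0.64/2 = 0.96, so exp(−0.96²/6.14) = 0.861.
- Contrast in a null region: 1.596 × 0.411 × 0.861 = 0.56 SD, where the truth is 0.

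The simulations estimated each participant's decoder and used a random-effects test on 35 people. At correlations of 0.3 and 0.6, shrinkage and diagonal decoders falsely flagged 97–100% of the 17 null regions, with spurious contrasts of 0.10–0.83 SD. An unregularised discriminant flagged about 4–8%, and stimulus labels about 3–6%. With no correlation between regions, every decoder stayed near 5%.

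**6. Inflation of a true effect.** Region A responds at 0.8 SD. Region B does not respond and correlates 0.6 with A. The discriminant weights are 1.25 and −0.75. The score has mean ±0.5 and SD 1, and A's expected value given score s is 0.8·s. The contrast for A is 0.8 × 2 × E|s|, where E|s| = √(2/π)·e^(−0.125) + 0.5 × (2Φ(0.5) − 1) = 0.704 + 0.191 = 0.896. That gives 1.43 SD, and simulation agrees (1.43 decoded, 0.80 by stimulus). In the three-responder setting the same 0.8 SD reads as 0.91–1.37 SD.

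**7. A used region that shows nothing.** Region B has decoder weight −0.75 but r = 0, so its contrast is 0.00 SD. It was rejected in 8% of 60 runs under either labelling.

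**The case against.** The strongest reply is that circularity is inferred. G2 states no labelling rule. F2 describes the decoder's output as a continuum, which fits two named classes poorly, and the exploratory EEG work in F2 does separate stress from calm by the environment shown. If G2 means the same, and uses only scans outside feedback, nothing is circular. That stands as a limit on the claim. It does not settle the text, since F2 places the determination of two states directly after decoder training, and G2 excludes no feedback scans.

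Four stronger readings are tempting and are not supported.
- A reader might infer that every region the decoder uses must differ. Step 7 is a counterexample, and section D itself distinguishes regions critical to discrimination from the most active ones.
- A reader might infer that group maps are bound to be false. F2 describes training on the individual's own brain states, and with person-specific decoders a random-effects test on pure noise keeps its nominal error.
- A reader might infer that the threat setting goes unused. It defines the scanning conditions and may supply the training labels; it is only not named in G2. It is also independent of brain activity only outside the feedback loop.
- A reader might fault the use of two classes instead of graded levels. That is a preference: F2 sets stimulus parameters for each participant, so a software level need not be a common scale across people.

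The reply is also right that this is a secondary analysis in a pilot.

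**Conclusion.** The concern holds conditionally. G2 leaves the labelling rule open, and the most natural reading of F2 makes the labels a product of the same scans. On that reading, within-person false positives and true effect sizes are inflated: 61% against 5%, and 1.43 SD against 0.80 SD, under the stated assumptions. At group level the damage ranges from none to nearly every non-responding region, depending on the decoder, the correlation between regions and the group model, none of which the plan specifies. Labelling by scene leaves the same problem in feedback sessions, which are 33% to 86% of a participant's sessions.

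The percentages illustrate the mechanism and do not forecast this trial's results. They assume independent volumes, a linear decoder and equal correlation between regions. The CAPS analysis is unaffected.

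**What to change.** In G2:
- Define Threat and Non-Threat by the experimenter-set stimulus condition.
- Restrict the analysis to scans where that condition was fixed in advance and not driven by the thermometer, that is, the non-feedback sessions.
- Test at group level with participant as a random effect, and state how multiple regions are handled.
- If decoder-defined maps are also wanted, take the labels from a decoder trained without the tested region and session, and report the maps as descriptive only. Leaving the region out is not a full cure, because a region correlated with those the decoder uses still has r above 0 in step 2.

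A graded threat regressor is optional.

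The cost is a few lines of text and a saved record of stimulus timing and condition for each scan, which should be arranged before scanning because it may not be recoverable later. Fewer scans enter this analysis: one or two sessions per participant. The maps will probably look less striking.
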